#### **9.2.4 Analysis of Secondary and Exploratory Outcomes**

This study is designed to test the primary hypothesis; however, it also offers the opportunity to evaluate important additional secondary and exploratory outcomes. Continuous secondary endpoints will be summarized by the mean and standard deviation with corresponding 95% confidence intervals. Categorical endpoints will be summarized by the sample proportions with exact or asymptotic confidence intervals. For time to event analyses, we will construct Kaplan Meier curves. Our analyses will consider sex as a biological variable that may affect treatment outcomes for COVID-19.

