# 1. Protocol Summary

## 1.1 Brief Synopsis

Title	Clinical-trial of COVID-19 Convalescent Plasma in Outpatients (C3PO)
Protocol Number	Pro00044489
Phase	Phase III
Methodology	Multi-center, randomized, single-blind, two-arm, placebo-controlled trial with blinded outcome assessment.
Study Duration	June 2020 to July 2021
Study Center(s)	SIREN Trial Network
Objectives	
Primary: To determine the efficacy and safety of a single dose of convalescent plasma (CP) for preventing the progression from mild to severe COVID-19 illness.
 
Secondary: Characterize the immunologic response to CP administration.

Endpoints	
Primary:
 
Disease progression defined as death or hospital admission or seeking emergency or urgent care within 15 days of randomization.
 
Secondary:
 
 
• Worst severity rating on the WHO's COVID Ordinal Scale for Clinical Improvement during the 30 days following randomization
 
• Time to disease progression on the COVID Outpatient Ordinal Outcome Scale censored at 15 days after randomization.
 
• Hospital-free days during the 30 days following randomization
 
• All-cause mortality at 30 days
 

	
 
• Symptom inventory measured using the CDC list of COVID-19 symptoms on days 2, 4, 6, 8, 10, 14, 15, 30
 
• Neutralizing antibody titers at days 0 (pre-intervention and post-intervention), 15, and 30
 
• Spike protein IgG antibody titers pre and post CP administration
 

Number of Subjects	Original planned maximum sample size: 600 (300 per arm) Revised maximum sample size based on planned re-estimation: 900 (450 per arm)
IND Sponsor	[name], MBA
Main Inclusion Criteria	
 
• One or more symptoms of COVID-19 illness and laboratory-confirmed SARS-CoV-2 infection.
 
• Has at least one study defined risk factor for severe COVID-19 illness
 
• Clinical team deems stable for outpatient management without new supplemental oxygen
 
• CP available at the site at the time of enrollment
 
• Duration of symptoms <math>\leq</math> 7 days at ED presentation and randomization
 
• Informed consent from subject
 

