### *Clinical studies:*

In both SARS and MERS outbreaks, the high mortality and absence of effective therapies led to the use of convalescent plasma in human studies. The largest study involved the treatment of 80 patients in Hong Kong with SARS. Patients treated before day 14 had improved prognosis defined by discharge from hospital before day 22, consistent with the notion that earlier administration is more likely to be effective. In addition, those who were RT-PCR positive and seronegative for coronavirus at the time of therapy had improved prognosis. There is also some anecdotal information on the use of convalescent plasma in seriously ill individuals. Three patients with SARS in Taiwan were treated with 500 ml of convalescent plasma, resulting in a reduction in plasma virus titer and each survived. Three patients with MERS in South Korea were treated with convalescent plasma, but only two of the recipients had neutralizing antibody in their plasma. The latter study highlights a challenge in using convalescent plasma, namely, that some who recover from viral disease may not have high titers of neutralizing antibody. Consistent with this point, an analysis of 99 samples of convalescent sera from patients with MERS showed that 87 had neutralizing antibody with a geometric mean titer of 1:61. This suggests that antibodies decline with time and/or that only some patients make high titer responses. It is also possible that other types of non-neutralizing antibodies are made that contribute to protection and recovery as described for other viral diseases.

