## 6.2 Preparation/Handling/Storage/Accountability

NHLBI is collaborating with BARDA who will contract with Vitalant to provide up to 500 units of CP with known titers of neutralizing SARS-CoV2 antibodies of 1:160 or higher for this trial. The supplier (Vitalant) has already collected many units of CP. Donors will meet current FDA eligibility requirements for COVID-19 Convalescent Plasma (<https://www.fda.gov/vaccines-blood-biologics/investigational-new-drug-ind-or-device-exemption-ide-process-cber/recommendations-investigational-covid-19-convalescent-plasma>)

1. COVID-19 convalescent plasma will be collected from individuals who meet all donor eligibility requirements.
2. COVID-19 convalescent plasma is collected from individuals who meet all of the following qualifications:
  - a. A positive serological test for SARS-CoV-2 antibodies after recovery.
  - b. Complete resolution of symptoms at least 14 days before the donation. A negative result for COVID-19 by a diagnostic test is not necessary to qualify the donor.
  - c. Male donors, or female donors who have not been pregnant, or female donors who have been tested since their most recent pregnancy and results interpreted as negative for HLA antibodies.

Serologic testing will be performed using state-of-the-art research methods. Specifically, CP will be tested using a chemiluminescent test for IgG and IgM against spike protein (Ortho VITROS Anti-SARS-CoV2 Total) or equivalent assay. This assay has been granted FDA Emergency Use Authorization (EUA). If this qualitative test is positive, then the CP is also tested with the Vitalant Research Institute SARS-CoV2 Reporter Viral Particle Neutralization (RVPN) test or equivalent assay. The presence of antibodies are generally confirmed within 48 hours of donor collection. Assays will be conducted by a central laboratory and assays will also be made available to

study investigators. The CP is labeled with the titer from the RVPN test as: negative, <1:40, positive 1:40, 1:160; 1:640, 1:2560, 1:10240, >1:10240. We do not intend to use CP with 1:40 or <1:40 titer.

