### **8.1.4 Blood Sample Storage, Processing and Shipping for Antibody Titer Testing**

Each site will ship the 4 blood samples from each participant to the central testing laboratory (University of Pittsburgh). The site can ship all of the samples for one participant together in a single package. Labels for samples with barcodes will be provided to sites in advance in order to ensure accurate sample tracking. Labeling samples with the subject ID from WebDCU can serve as a backup procedure.

*Antibody titres:* To determine the immunologic response to CP administration, we will measure anti-SARS-CoV-2 IgG, IgM and neutralizing antibody titres pre-intervention, post-intervention and at days 15 and 30.

Testing will be identical to the testing performed to determine the titer of the donor CP. We will determine the IgG/IgM titers to SARS CoV-2 S (Spike) protein using enzyme linked immunoassays (BSL-2+). There are multiple assays available and in development. We will compare titres from the Vitalant (Ortho VITROS Anti-SARS-CoV2 Total) assay to titres from other assays (e.g. Euroimmun ELISA) whenever possible to determine the concordance. In a subset of these samples, we will measure antibody neutralization titers using the gold standard assay, a viral plaque assay performed in a BSL-3 facility at University of Pittsburgh. This will allow us to determine whether high titers in binding assays actually represent superior neutralization capacity for inhibiting SARS-CoV-2 infection.

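### Section 9.2.4 gives antibody titers no log-scale analysis and no rule for open-ended values; its default of mean and SD suits a four-fold titer scale poorly

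*Combined protocol and SAP*

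**What the plan says.** Section 9.2.4 covers secondary and exploratory outcomes together; after stating that the trial is designed for the primary hypothesis, it adds that "it also offers the opportunity to evaluate important additional secondary and exploratory outcomes". For continuous endpoints it says "Continuous secondary endpoints will be summarized by the mean and standard deviation with corresponding 95% confidence intervals". For categorical endpoints it says "Categorical endpoints will be summarized by the sample proportions with exact or asymptotic confidence intervals". Time-to-event outcomes get Kaplan-Meier curves. Nothing in the section is specific to titers, and no log transformation, geometric mean, fold change or rule for out-of-range results appears elsewhere.

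The titer endpoint is "Neutralizing antibody titers at days 0 (pre-intervention and post-intervention), 15, and 30". Section 1.1 lists it under secondary endpoints, and the heading of section 8.1.3 also calls the immunological endpoints secondary. The endpoint list in section 1.2 and section 3.3 place titers under exploratory.

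The only stated reporting scale is for donor units, in section 6.2: "The CP is labeled with the titer from the RVPN test as: negative, <1:40, positive 1:40, 1:160; 1:640, 1:2560, 1:10240, >1:10240". Section 8.1.4 links this to participants: "Testing will be identical to the testing performed to determine the titer of the donor CP". Sections 8.1.3 and 8.1.4 also name a lentiviral pseudovirus assay, ELISAs and a plaque assay (the last in a subset), without a reporting scale for any of them.

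When section 2.2 summarizes earlier convalescent sera, it uses the geometric mean: "87 had neutralizing antibody with a geometric mean titer of 1:61".

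**The concern.** Titers from serial dilution are multiplicative. On such a scale the arithmetic mean is driven by the few highest results, and a result reported only as below the lowest or above the highest dilution has no value to average. Someone has to choose a number for it, and the protocol does not say which.

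The immunologic response to plasma is the trial's only stated secondary objective. Section 2.3.1 raises an attenuated immune response as a theoretical risk, and section 8.1.3 intends the titers to show that the recipient's own response is not impaired. For that question an insensitive summary errs towards reassurance. An unstated substitution rule also leaves room for choices made after the data are seen.

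**Working it through.** The protocol gives no titer SD, target difference or power, so there is no stated figure to reproduce.

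**Weight of high results.** 10240 / 40 = 256. One result at the top labelled dilution counts in an arithmetic mean as much as 256 results at the lowest.

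**Results with no number.** Assume log-normal titers with log10 SD 0.6. With a geometric mean of 160, the share below 1:40 is Φ((log10 40 − log10 160)/0.6) = Φ(−1.00), about 16%. With a geometric mean of 80 it is Φ(−0.50), about 31%.

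**Inputs for the power check**
- Sample: 450 per arm (revised maximum, sections 1.1 and 1.2) × 0.90 (follow-up target above 90%, section 7.2) = 405 per arm. That samples track follow-up is an assumption.
- Subset: the size of the plaque-assay subset is not stated; 100 per arm is assumed.
- Geometric mean in the higher arm: 160, 640 or 2560 (assumed). The other arm has half that.
- log10 SD: 0.6, 0.8 or 1.0 (assumed). As a rough anchor, if 1:40 to 1:10240 (log10 256 = 2.4 units) spans about 4 SD, then SD is about 2.4/4 = 0.6.

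**Method.** Draw log-normal titers and record each as the highest four-fold step it reaches. Set <1:40 to 20 and cap >1:10240 at 10240. Compare arms with a Welch test at two-sided 0.05, once on recorded titers and once on their logs. Each cell has 4,000 simulated trials; repeat runs agreed within about three percentage points.

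Percentage of trials detecting a halving, for geometric means 160 / 640 / 2560:

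| Per arm | log10 SD | Raw mean | Log scale |
|---|---|---|---|
| 405 | 0.6 | 96 / 100 / 100 | 100 / 100 / 100 |
| 405 | 0.8 | 80 / 95 / 99 | over 99 in each |
| 405 | 1.0 | 69 / 86 / 94 | 97 / 98 / 99 |
| 100 | 0.6 | 57 / 61 / 78 | 90 / 92 / 92 |
| 100 | 0.8 | 31 / 43 / 57 | 68 / 72 / 72 |

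In these settings the highest 5% of participants supply roughly 14% to 55% of the arm total.

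**Effect of the invented number.** With 405 per arm, geometric mean 640 and SD 1.0, raw-mean detection is 86% if >1:10240 is entered as 10240 and 69% if it is entered as 40960, one step higher. On the log scale it is 98% either way.

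**The case against.** The case against is substantial, and much of it stands.

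- **Status.** The quoted rule is for continuous secondary endpoints, and two sections call titers exploratory. So titers reach the rule only by default. If they do not reach it, however, they have no continuous rule at all, and the gap remains.
- **Categorical reading.** Stepped titers could be summarized as proportions, which would accept the open-ended labels directly; section 9.2.1 already plans titer categories for donor units. But proportions give no fold change, and section 3 asks about the change from before to after plasma.
- **Scale.** The four-fold labels are stated for donor units and reach participants only through section 8.1.4. Other participant assays may report differently. This limits the numerical illustration, not the need for a rule.
- **Descriptive purpose.** Section 9.2.4 speaks of summaries and specifies no between-arm titer test. The power figures therefore measure relative efficiency; they do not show that a planned test fails.

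Two stronger readings are tempting. A reader might infer that the trial would generally miss a halved response. The documents do not support that: at about 405 per arm and SD 0.6, raw means still detect it in at least 96% of runs. Simulating an uncapped log-normal would look worse, but would contradict the capped scale used here. A reader might also infer that arithmetic means hide the 1-hour rise after one unit. By the rough 60-fold dilution in section 2.2, units of 1:160 and 1:640 add about 160/60 = 2.7 and 640/60 = 10.7, both below the 1:40 floor, so a log transformation would not recover them either.

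**Conclusion.** The point holds as a gap in specification with a clearly better method available. The only rule for continuous outcomes is arithmetic mean and SD. It cannot take open-ended titers without invented values, and it gives great weight to the highest results.

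At the full sample the loss is negligible at log10 SD 0.6 or below, and material at about 0.8 or above, chiefly where geometric means are low. In an assay subset of about 100 per arm it already appears at SD 0.6. These sizes rest on an assumed SD, geometric mean, log-normal shape and subset size, none of which the documents supply. The secondary immunologic objective is exposed; the primary analysis is not.

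**What to change.** Add a paragraph to section 9.2.4 stating that:

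1. Titers are analysed on the log scale and reported as geometric mean titers, between-arm ratios and within-person fold changes, each with a 95% interval.
2. Results beyond the lowest or highest dilution are treated as censored, with a simple named substitution as a sensitivity analysis.
3. The proportion below the floor is reported by arm and visit.
4. For each participant assay, the reporting scale and limits are named.

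Also settle whether titers are secondary or exploratory, and make sections 1.1, 1.2, 3.3 and 8.1.3 agree.

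The cost is a paragraph of text and a consistency edit, with no new samples or data. There is one small downside: a censored-normal model may fit poorly at Day 0, where seronegative and seropositive participants may be mixed. The proportion below the floor should be read alongside it.

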### **Secondary Endpoints**

- Worst severity rating on the WHO's COVID Ordinal Scale for Clinical Improvement during the 30 days following randomization
  - Death
  - Hospitalized on invasive mechanical ventilation or ECMO
  - Hospitalized on non-invasive ventilation or high flow nasal cannula
  - Hospitalized on supplemental oxygen
  - Hospitalized not on supplemental oxygen
  - Not hospitalized with limitation in activity (continued symptoms)
  - Not hospitalized without limitation in activity (no symptoms)
- Time to disease progression on the COVID Outpatient Ordinal Outcome Scale censored at 15 days after randomization
  - Patient requires care in the hospital
  - Patient requires care in the ED or urgent care
  - Patient at home with symptoms rated as moderate (defined as fever, shortness of breath, abdominal pain)
  - Patient at home with symptoms rated as mild (defined as afebrile, constitutional symptoms (flu-like illness) without shortness of breath)
  - Patient in their usual state of health
- Hospital-free days during the 30 days following randomization
- All-cause mortality at 30 days

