#### 8.1.2 Secondary Endpoints (clinical)

These endpoints can be ascertained from the subject or informant report during follow-up calls, supplemented by review of health records. Surveys and assessments from day 0-14 that are completed within 1 day of the time point will be counted as qualifying and not considered missing (for example day 4 assessment may be done on day 4 or 5).

**COVID-19 illness severity:** We will quantify COVID-19 illness severity using a 8-point ordinal scale developed by a World Health Organization (WHO) committee. We will record the worst illness severity rating observed during the 30 days following randomization:

WHO's COVID Ordinal Scale for Clinical Improvement

- 8 = Death
- 7 = Hospitalized, intubated, mechanically ventilated and requiring additional organ support (pressors, renal replacement therapy)
- 6 = Hospitalized, intubated and mechanically ventilated
- 5 = Hospitalized on non-invasive ventilation or high flow nasal cannula
- 4 = Hospitalized on supplemental oxygen by mask or nasal prongs
- 3 = Hospitalized not on supplemental oxygen
- 2 = Not hospitalized with limitation in activity (continued symptoms)
- 1 = Not hospitalized without limitation in activity (no symptoms)

*COVID-19 illness severity (outpatient):* An adaptation of the WHO scale, based on the quality of symptoms reported by the subject, can quantify outpatient disease severity among patients at home (scores 1-2 on the WHO scale). This 5-point COVID Outpatient Ordinal Outcomes scale was adapted for outpatient use from Harrell 2020

(<http://hbiostat.org/proj/covid19/bayesplan.html>). This scale is hierarchical where 1 is the highest severity (hospitalization) and 5 is the lowest severity.

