### 9.1 Sample Size

Sample size is restricted by the availability of CP for the participating sites. Based on discussions with the NHLBI, we are assured to have sufficient CP available for roughly 300 patients at the time of study initiation.

Therefore, we provide power estimations based on our primary outcome, assuming a maximum of 600 randomizations (300 per group).

Figure 1 provides a range of risk differences (control minus treatment) based on potential event rates for our control population. For example, if the primary outcome event proportion within 15 days from randomization is 20% in the control population, then we have 85% power to detect an absolute decrease of at least 10% in this proportion for those treated with CP. If the control proportion is less than 20% then we can detect differences of roughly 8% while maintaining more than 80% power. Alternatively, if the control rate is closer to 30%, then our power begins to drop for detecting risk differences less than 10%. Based on the current information on hospitalizations in this COVID population, we do not expect the proportion in the standard of care arm to vary greatly from 20%. Clinicians are unlikely to discharge patients whose risk for the primary outcome is significantly greater than 30%..

[figure not shown]

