### 9.2 Analysis Plan

#### 9.2.1 Primary Analysis

Outcomes will be analyzed using the intent-to-treat principle (ITT). The primary analysis for this trial is to test the hypothesis of superiority of CP as compared to saline in the ITT population. To

test this hypothesis, the posterior probability that the proportion of primary outcome events at 15-days post randomization is higher in the saline arm as compared to the CP arm will be calculated. Because little is known about the impact of CP, we assume a non-informative beta distribution for the prior probability. The primary null hypothesis (that the CP proportion is greater than or equal to saline) will be rejected if the posterior probability is greater than or equal to 0.975 (selected to coincide with a one-sided alpha level of 0.025 under a frequentist design). The treatment effect and corresponding credible interval will be constructed.

If the trial fails to enroll the planned sample size due to a significant decrease in the number of COVID-19 patients, then Bayesian posterior and predictive probabilities will be used to assist in the interpretation of the observed data.

Secondary analyses of the primary outcome will explore the impact of potential prognostic variables including age, sex, onset of symptoms duration and site. A logistic regression model will be used for these additional analyses. We will also examine whether participants' pre-treatment antibody levels and/or the genotype of the SARS-CoV2 virus that they carry modify the association between CP and outcome.

The inherent variability in antibody titer among CP units will provide an important opportunity to explore the dose-effect relationship for CP. We envision performing a similar regression of the primary outcome using CP titer categories.

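### Section 9.2.4 pre-specifies no between-arm effect measure for WHO worst severity or time to progression, and the WHO level list differs between sections

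*Combined protocol and SAP*

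**What the plan says.** On analysis, Section 9.2.4 states for categorical endpoints: "Categorical endpoints will be summarized by the sample proportions with exact or asymptotic confidence intervals". For the other endpoint at issue it states: "For time to event analyses, we will construct Kaplan Meier curves". Nothing further is said about comparing the arms on either one. Continuous endpoints likewise get means, standard deviations and intervals.

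On the scale, Section 8.1.2 says "We will quantify COVID-19 illness severity using a 8-point ordinal scale" and numbers the levels 1 to 8. Synopsis 1.2 lists seven levels for the same endpoint, with one for "Hospitalized on invasive mechanical ventilation or ECMO". Section 3 lists eight.

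On purpose, the objectives table in Section 3 pairs both endpoints with learning what effect CP has on severity. By contrast, Section 9.2.1 promises a treatment effect with a credible interval for the primary outcome, and logistic regression for secondary analyses of it.

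**The concern.** A comparative objective needs a named contrast. Without one, the estimate of the effect on severity has to be chosen later, among several reasonable options that need not agree. This can matter before the final analysis. Under Section 9.2.2, if a boundary is crossed the DSMB report also includes secondary outcomes, and they inform the stopping recommendation. Whoever prepares that report would be choosing the contrast with unblinded data in hand.

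Two further points follow. Separate proportions for each level ignore the ordering of the scale and leave very small counts at the severe end. And no ordinal analysis can be reproduced while the sections disagree about what the levels are.

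**Working it through.** **1. The plan's own figures.** The documents give no power, effect size or alpha for any secondary endpoint, so there is nothing to reproduce on this point. The only power example with stated rates concerns the primary outcome. For 300 per arm and a control rate of 20%, Section 9.1 says "then we have 85% power to detect an absolute decrease of at least 10% in this proportion for those treated with CP". A fixed-sample two-proportion formula at one-sided 0.025 gives 93.1% for 20% vs 10%. With the futility rule treated as binding at the 33/50/75% looks, simulation gives 87.6%. Futility stopping may explain the lower stated figure. That is a separate matter and does not bear on this point.

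**2. The level lists side by side.**

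| Place | Levels | Ventilated with pressors or renal replacement | ECMO |
|---|---|---|---|
| 1.2 | 7 | no separate level | with invasive ventilation |
| Section 3 | 8 | own level, just below death | with invasive ventilation |
| 8.1.2 | 8 | level 7 | not mentioned |

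A ventilated patient on pressors shares a level with all ventilated patients under 1.2, but ranks above them under Section 3 and 8.1.2. Under 8.1.2 a ventilated ECMO patient could be read as level 6, or as level 7 if ECMO counts as additional organ support.

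**3. Efficiency on the ordinal scale.** The documents give neither a level distribution nor an odds ratio, so these are assumptions: 450 per arm (the revised maximum), and controls at levels 1 to 8 of 2/86/5/4/1.2/0.6/0.4/0.8%, which is 12% hospitalized. The expected control counts at levels 5 to 8 are then 5.4, 2.7, 1.8 and 3.6. A common odds ratio (OR) below 1 favours CP at every cut, with a two-sided 0.05 test (one-sided 0.025).

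At OR 0.5 the hospitalized proportion on CP has odds 0.5 × 0.12/0.88 = 0.0682, which is 6.4%. The symptom-free share moves from 2% to 3.9% (odds of level 2 or worse fall from 49 to 24.5).

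- Proportional odds (Whitehead): power = Φ(|ln OR|·√V − 1.96), with V = N(1 − Σp̄³)/12. Here N = 900 and 1 − Σp̄³ = 0.322, so V = 24.1 and power = Φ(0.693 × 4.91 − 1.96) = Φ(1.45) = 0.93.
- Hospitalized or not: (0.0562 − 1.96 × 0.01926)/0.01917 = 0.96, so power = Φ(0.96) = 0.83.

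Simulation with a tie-corrected rank test gives the figures below. Repeat runs differ by up to about 0.02.

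| OR | Ordinal | Hospitalized or not |
|---|---|---|
| 0.5 | 0.91 | 0.83 |
| 0.67 | 0.50 | 0.43 |
| 0.75 | 0.30 | 0.27 |

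Merging levels 1 and 2 while keeping the order of levels 3 to 8 gives 0.835 at OR 0.5, the same as the binary cut. The gain here therefore comes entirely from the symptom versus no-symptom split, not from ordering the inpatient levels.

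Other assumed control distributions, at an OR of 1.5 in favour of CP (about 0.67 on the scale above), 450 per arm:

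| Hospitalized / symptomatic / symptom-free | Ordinal | Hospitalized or not | Information kept by the cut |
|---|---|---|---|
| 10 / 85 / 5 | 0.58 | 0.39 | 70% |
| 15 / 75 / 10 | 0.76 | 0.52 | 66% |
| 20 / 50 / 30 | 0.90 | 0.62 | 57% |
| 10 / 60 / 30 | 0.87 | 0.39 | 36% |

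The gap is widest when many patients are symptom-free throughout. Section 5.1 requires at least one symptom at entry, which makes a large symptom-free share on a worst-rating scale less likely. That is an inference, not something the plan states.

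**4. Time to progression.** Proportional hazards and 300 per arm are assumed. For 20% vs 10% by day 15, HR = ln 0.9/ln 0.8 = 0.472 and events = 300 × 0.30 = 90. Log-rank power = Φ(√90/2 × 0.750 − 1.96) = Φ(1.60) = 94.5%. The day-15 difference gives (0.10 − 1.96 × 0.02915)/0.02887 = 1.48, or 93.1%. For 30% vs 20% the pair is 81.9% and 80.9%. For 50% vs 40% it is 70.8% and 69.3%. The gap is 1 to 2 points.

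**The case against.** The strongest reply is that Section 9.2.4 says the study is designed to test the primary hypothesis. Secondary results are supportive, and describing them is a legitimate choice. Section 9 also explains why the primary comparison uses proportions: timing is driven more by the course of illness than by treatment, and delay alone is judged unimportant if the same share progress. That makes a plain Kaplan-Meier display defensible. Both arguments stand. They keep this point at the level of a cheap improvement and mean a hazard ratio should not be the only option offered. They do not supply the missing contrast for a comparative objective, and they do not touch the conflicting level lists.

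A reader might infer three stronger things, none of which the documents support:

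- That summaries will be within-arm only. Section 9.2.4 does not say whether its intervals are per arm or for a difference.
- That most of the power is lost. A descriptive summary has no power of its own, the ordinal gap is 8 points in the main scenario at OR 0.5, and the gap for time to progression is 1 to 2 points.
- That arms will be judged by whether per-arm intervals overlap at some inpatient level. That rule would succeed only about 27% of the time at OR 0.5, but it appears nowhere in the plan.

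**Conclusion.** The point holds in a limited form. It rests on the text, without any assumption, that no between-arm effect measure is pre-specified for the two endpoints although their objective is comparative, and that three current sections define the WHO scale differently. The efficiency argument is secondary and depends on assumed inputs: about 3 to 8 points of power in the main scenario, more if a sizeable share of patients are symptom-free throughout, and little for time to progression. The primary conclusion is unaffected.

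**What to change.** - **Scale.** Reconcile the lists in 1.2, Section 3 and 8.1.2 into one eight-level scale, with ECMO assigned explicitly to a level.
- **Worst severity (9.2.4).** Report a common odds ratio with a 95% interval from a proportional-odds model with arm and age. Enter site as a random effect or omit it, because at least 30 sites are planned and the severe levels will be sparse. State a check of proportional odds and a rank-based fallback.
- **Time to progression (9.2.4).** Report one between-arm effect with a 95% interval: a hazard ratio, or the day-15 Kaplan-Meier difference, which sits better with the reasoning in Section 9. Choose one in advance.
- **Displays and status.** Keep the planned proportions and curves as displays. State that all these analyses are supportive, with no alpha allocated.

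The cost is some SAP wording, a little more programming and a modelling assumption to check. No new data are needed.
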